### Inclusion criteria

ALHIV aged 13-19 years who are aware of their HIV status for at least six months before enrolment (i.e., know the infection by its name and understand some of its implications).

ART initiation of not less than 6 months.

**Adolescents aged 13-19 with viral load threshold of <1000/uL.**

ALHIV accessing ART within the participating clinics.

Healthcare workers with direct contact with ALHIV and have been involved in viral load result counselling in participating clinics.

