**The specific objectives are:**

1. To determine viral load fluctuation between routine annual VL testing and the extent to which annual VL using DBS reflects short term fluctuations that occur in the interim.
2. To determine what proportion of ALHIV with VL <1000 copies/uL on DBS have a plasma VL less than 200 copies/uL
3. To explore the reasons for and adolescent's understandings of fluctuations in VL and what a VL<1000 copies/mL means to ALHIV

**Methods:** This mixed method study will be conducted in conjunction with key stakeholders. We will enrol 300 ALHIV with a recent VL<1000 copies/uL in three HIV clinics in Harare and follow them for 12 months. Of these, 100 will be randomly selected to undergo repeat VL testing, using both DBS and plasma samples at enrolment, 6 and 12 months. A purposive sample of twenty will be selected for a longitudinal qualitative study. Additionally, up to eight participatory workshops will be conducted with key stakeholders over the course of the study to co-develop a 'safe' way to message U=U for LIC.

**Potential impact:** The study will provide scientific evidence on whether routine VL testing using DBS as available in LIC can provide sufficiently robust evidence of 'undetectability' and on the variability of an individual's virological response over 12 months. It will provide contextually orientated evidence to inform U=U messaging which has the potential to change the motivation of ALHIV to engage with their treatment and care.

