### Research question

The main research question for this study is:

Can messaging relating to Undetectable (viral load) = Untransmissible (virus) change the motivations and adherence of adolescents living the HIV in Africa?

The study therefore aims to answer three key questions: i) what is the evidentiary robustness of a VL 1000c/uL measured using a DBS sample to be considered 'undetectable? ii) what are the perceived risks and opportunities of incorporating U=U into routine HIV treatment and care for adolescents in LIC and iii) can locally acceptable and appropriate ways to integrate the discussion about undetectability into standard of care for ALHIV be developed for Zimbabwe in partnership with stakeholders?

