### Aim

The study aims to provide scientific evidence on whether routine VL testing using DBS as available in LIC can provide sufficiently robust evidence of 'undetectability' and on the variability of an individual's

virological response over 12 months and between those considered undetectable (<1000) and those undetectable and untransmissible (<200). We therefore propose to conduct a longitudinal study to i) determine at what 'threshold' U=U might be safely promoted in this setting; ii) explore ALHIV's understanding and or interpretation of the VL results. The study will also explore responsible ways to disseminate this message to ALHIV living in Zimbabwe, and across the Southern African region.

Our specific objectives are:

1. To determine viral load fluctuation between routine annual VL testing and the extent to which annual VL using DBS reflects short term fluctuations that occur in the interim.
2. To determine what proportion of ALHIV with viral load <1000 copies/uL on DBS have a plasma VL less than 200 copies/uL
3. To explore the reasons for and adolescent's understandings of fluctuations in VL (measured using standard of care DBS) and what a VL<1000 copies/mL means to ALHIV
4. To explore the perceived risks and opportunities of incorporating U=U into routine HIV treatment and care for ALHIV in LIC
5. To explore with key stakeholders the implications of our findings for the feasibility and framing of the U=U message in LIC for ALHIV.

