### Study design and setting

A longitudinal mixed method study will be conducted in Harare City Health Department at three high volume clinics (BRIDH, Kuwadzana and Rujeko). All the clinics provide care as part of the Paediatric Opportunistic Infection and Antiretroviral Therapy program (OI/ART) and started conducting routine viral load testing in 2016. BRIDH has capacity for onsite VL testing. The three clinics are situated in the low-income and overpopulated residential suburbs which are ranked among the poorest residential areas in Harare (Mbare, Kuwadzana and Dzivarasekwa). The clinics mainly serve people from poor households. BRIDH is located in Mbare residential suburb which is one of the oldest and most impoverished residential suburbs in Zimbabwe.

**Aim 1 and 2: To determine viral load fluctuation between routine annual VL testing and the extent to which annual VL using DBS reflects short term fluctuations that occur in the interim and to determine what proportion of ALHIV with viral load <1000 copies/uL on DBS have a plasma VL less than 200 copies/uL**

The study will explore the sensitivity of viral load testing so that decisions can be made on the best use of resources in optimizing the care and support that can be given to ALHIV in the region. This component will utilize primary and secondary data. Three hundred ALHIV with a recent VL<1000 copies/uL will be randomly selected from clinic registers complete a structured questionnaire. Interviews will explore demographic characteristics, self-reported ART adherence and knowledge of U=U. In depth analysis of ALHIV' VL trajectories will be conducted on a randomly selected sub sample of 100 ALHIV using 6 monthly finger prick DBS and plasma VL sampling to provide evidence on the fluctuation in an individual's virological response over 12 months and how this differs between those considered virologically suppressed (<1000 copies/uL) and those undetectable and untransmissible (<200 copies/uL). Secondary data will be collected from clinic records on HIV treatment history, drug regimens, VL testing (include VL at enrolment and 12 months).

**Aim 3: To explore the reasons for and adolescent's understandings of fluctuations in VL (measured using standard of care DBS) and what a VL<1000 copies/uL means to ALHIV.**

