A purposive and theoretical subsample of 20 ALHIV will be selected to participate in longitudinal qualitative interviews at enrolment, 6 and 12 months after receiving their VL result. The subsample will be selected from the quantitative sample. Theoretical sampling is defined as interviewing directed by evolving themes rather than focusing on predetermined populations. Purposive and theoretical sampling are strategies employed to ensure that the participants involved have a wide range of experiences, relevant to answering the research question, but also limit the scale of the data collection so that detailed analyses could be conducted. Interesting dynamics such as duration on ART, current regimen (first/second line), mode of transmission among other things will be considered among other characteristics.

Interviews will explore reasons for consistent/fluctuating VL and their understandings of why and what is happening. We will explore whether having a VL<1000copies/uL motivates them to adhere and whether and how learning that they have a fluctuating or high VL affects their subsequent motivation to adhere and or their wellbeing, as well as the influence, if any, on their experience of HIV stigma. The interviews will also explore what being undetectable means for ALHIV and what influence it has, if any, on their adherence motivation and behaviour alongside developing a broader understanding of the effects of social context, including events in their daily life, on their engagement with and adherence to ART and their understandings of the social meanings of living with HIV. These in-depth interviews will also explore whether and how learning that they have a fluctuating or high VL affects their subsequent motivation to adhere and or their wellbeing, as well as the influence, if any, on their experience of HIV stigma. Interpretations of how the VL results are described to ALHIV by clinic staff will also be explored. Data collection will be an iterative process, where all the interviews will be transcribed and translated in order to inform individualized guides for subsequent in-depth interviews.

**Aim4: To explore the perceived risks and opportunities of incorporating U=U into routine HIV treatment and care for ALHIV in LIC**

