## Procedures

### Quantitative interviews

The sample size for ALHIV will be calculated with reference to the total number of ALHIV aged 13-19 years on ART with a VL <1000copies/uL taken within 6 weeks of study launch from the 3 sampled clinics according to the clinic records. A list of all ALHIV aged 13-19 on ART will be drawn from the ART registers from this, a systematic random sample will be selected to recruit 300. The sample sizes will be calculated using a margin of error of 5 %; confidence interval of 95% and response distribution of 50% (<http://www.raosoft.com/samplesize.html>). The figure obtained will be shared among the 3 clinics using Probability Proportionate to Size (PPS) sampling. ALHIV taking account age, recency of disclosure, duration on ART and current ART regimen and will be shared among the three clinics using Probability Proportionate to Size (PPS) as in figure 1 below.

[figure not shown]

Figure 1: Recruitment flow chart

The quantitative subset of 100 ALHIV who will have intensive follow up and will provide plasma and DBS samples VL testing at enrolment, 6 and 12 months will be randomly selected. Ideally, we wanted to have intense follow up on all 300 participants however due to limited resources we reduced the sample size for intense follow up to 100 participants.

Eligible participants will be drawn from the clinic records with the assistance of the clinic nurses. A list of potential eligible participants per clinic containing the residential suburb, name and contact details will be given to the Africaid Zvandiri Community Adolescent Treatment Supporters (CATS) working in the clinics for recruitment during regular support group meetings or through the phone. CATS are ALHIV aged 18-24 years who are trained by Africaid and MOHCC to provide support to other ALHIV. All the clinics are supported by Africaid and offer psychosocial support services to ALHIV through a combination of home visits and support groups. Willing participants will be invited to the clinic and will be introduced to the research team. After being given study information, interested participants who met the inclusion criteria and willing to provide written informed consent were recruited.

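### The 1000 viral load threshold is per microlitre in the inclusion criterion, sampling frame and Objective 2 but per millilitre in Objective 3, a 1000-fold conflict

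*Combined protocol and SAP*

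**What the plan says.** The eligibility rule under Inclusion criteria is "Adolescents aged 13-19 with viral load threshold of <1000/uL"; the word copies is missing. The sampling frame in Quantitative interviews is built from adolescents "with a VL <1000copies/uL taken within 6 weeks of study launch". The Abstract's methods state "We will enrol 300 ALHIV with a recent VL<1000 copies/uL in three HIV clinics in Harare". Objective 2 in the Aim section is "To determine what proportion of ALHIV with viral load <1000 copies/uL on DBS have a plasma VL less than 200 copies/uL", and its version in the Abstract uses the same units. The Research question asks "what is the evidentiary robustness of a VL 1000c/uL measured using a DBS sample", and the qualitative text in Study design and setting says "We will explore whether having a VL<1000copies/uL motivates them to adhere".

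Objective 3 is different. In both objective lists (Abstract and Aim) it asks "what a VL<1000 copies/mL means to ALHIV", directly below an Objective 2 stated per uL. The Aim 3 heading in Study design and setting returns to "what a VL<1000 copies/uL means to ALHIV".

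In Rationale, Aim, and Expected outcomes, the 1000 and 200 cut-offs also appear once each with no unit. The only other viral load figure with a unit is in Background and significance, where results from other studies are reported against 50 copies/ml.

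**The concern.** The same threshold carries two units that differ by a factor of 1000, and one objective carries both. This is not confined to background prose. The 1000 threshold decides who may be sampled and enrolled, and it forms the denominator of Objective 2. The 200 cut-off forms the numerator.

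Read literally, the inclusion criterion admits viral loads up to 1,000,000 copies/mL, while Objective 3 treats the threshold as 1000 copies/mL. The study also sets out to identify a threshold at which the U=U message could be promoted, and it plans to carry its findings into Ministry guidelines and patient materials. A wrong unit in the protocol could pass into those products.

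**Working it through.** There is no stated calculation to reproduce. The check is a unit conversion and a count of how each threshold is written.

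**Conversion**

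- 1 mL = 1000 uL.
- 1000 copies/uL × 1000 uL/mL = 1,000,000 copies/mL.
- 200 copies/uL × 1000 uL/mL = 200,000 copies/mL.
- Ratio to Objective 3: 1,000,000 / 1000 = 1000, and log10(1000) = 3.

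**Count by section**

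| Section | 1000 per uL | 1000 per mL | 1000, no unit | 200 per uL | 200, no unit |
|---|---|---|---|---|---|
| Abstract (objectives and methods) | 2 | 1 | 0 | 1 | 0 |
| Research question | 1 | 0 | 0 | 0 | 0 |
| Rationale | 0 | 0 | 1 | 1 | 1 |
| Aim | 1 | 1 | 1 | 1 | 1 |
| Study design and setting, Aims 1 and 2 and the Aim 3 heading | 4 | 0 | 0 | 2 | 0 |
| Study design and setting, Aim 3 text | 1 | 0 | 0 | 0 | 0 |
| Quantitative interviews | 1 | 0 | 0 | 0 | 0 |
| Inclusion criteria | 1 | 0 | 0 | 0 | 0 |
| Expected outcomes | 0 | 0 | 1 | 0 | 1 |
| **Total** | **11** | **2** | **3** | **5** | **3** |

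The 200 cut-off never appears per mL. The range of 200 to 1000 c/uL in the Rationale describes a cited study and is not counted.

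**Three readings of Objective 2**

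1. Both cut-offs per uL, as written: the proportion with plasma below 200,000 copies/mL among those with DBS below 1,000,000 copies/mL.
2. Both per mL: the proportion with plasma below 200 copies/mL among those with DBS below 1000 copies/mL.
3. Only the 1000 corrected to mL: the numerator cut-off becomes 200,000 copies/mL, which is 200,000 / 1000 = 200 times the denominator cut-off. Nearly everyone would meet it, and the objective would have almost no content.

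Readings 1 and 2 are different estimands. Reading 3 shows that the 200 cut-off has to move with the 1000 threshold, although no section gives it per mL. Its error is therefore inferred from its sharing a sentence and a unit with the 1000 in Objective 2.

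**What does not change**

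The sample-size inputs in Quantitative interviews (5% margin of error, 95% confidence, 50% response distribution) contain no viral load value and are unaffected.

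**The case against.** The strongest reply is that no informed reader would apply the literal uL reading. Study design and setting treats values below the 1000 threshold as virologically suppressed, other sections call them undetectable, and the Background reports results against 50 copies/ml. On the literal reading the threshold would be 1,000,000 / 50 = 20,000 times that figure. Participants are drawn from existing clinic records with the help of clinic nurses, so in practice the clinics' own unit would apply. Objective 2 uses one unit throughout, and the only per-mL uses are in a qualitative objective that sets no eligibility rule or numerical endpoint. No mis-enrolment or misclassified result has been shown. On this view the point is a notation error of modest weight, and a matter of consistency rather than of faulty arithmetic.

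Much of this stands. It is a consistency error, most likely a repeated slip, and its practical effect may be small. It is also fair that the range cited from another study in the Rationale should not simply be rewritten; its unit cannot be checked from the protocol.

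It does not remove the conflict. The argument relies on clinic records being in copies/mL, and the protocol states no reporting unit for DBS or plasma results. A majority reading of the text favours uL by 11 to 2. The internal consistency of Objective 2 does not help if both of its cut-offs are wrong by the same factor.

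**Conclusion.** The concern holds. The 1000 threshold is stated in two units that differ 1000-fold (3 log10), 11 times per uL and twice per mL, and nothing in the protocol reconciles them. The inclusion criterion, the sampling frame and both cut-offs of Objective 2 carry the unit that conflicts with Objective 3, so a decision threshold is ambiguous as written and must be corrected.

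The factor of 1000 is exact and rests on no assumption. That copies/mL is the intended unit is an inference from Objective 3 and the per-mL figure in the Background. For the 200 cut-off the inference is indirect. That the practical effect is small is an assumption that depends on how the clinics and the laboratory report results.

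**What to change.** State both thresholds in one unit throughout. Copies/mL is the unit consistent with Objective 3 in both objective lists and with the Background. If the authors confirm it, these places change:

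- Abstract: Objective 2 and the enrolment sentence.
- Research question.
- Rationale: the 200 cut-off.
- Aim: Objective 2.
- Study design and setting: the heading and text for Aims 1 and 2, the Aim 3 heading and the qualitative text.
- Quantitative interviews: the sampling frame.
- Inclusion criteria: the unit, and the missing word copies.
- Rationale, Aim and Expected outcomes: add the unit where 1000 and 200 have none.

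The authors should confirm the unit of the 200 cut-off, and check the 200 to 1000 range in the Rationale against its source before changing it.

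The protocol should also state the unit in which DBS and plasma results are reported. The same unit should be used for the viral load data field, its range check (Managing, storing and curating data) and the codebook (Metadata standards and data documentation). Those two sections contain no error; this step keeps the correction from being lost at data entry.

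The cost is a wording amendment, plus a check of the unit set in the database. Samples, visits and participant numbers do not change.

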### Exclusion criteria

Unable to provide informed assent/ and parental informed consent.

Requires urgent medical attention or has severe mental health problems that would invalidate the informed assent/consent process or else contraindicate participation.

### Data management and analysis procedures

Quantitative data will be collected on password protected and encrypted tablets. Qualitative interviews will be audio recorded; hand-written notes will be taken down as back-up. The Principal applicant will train, supervise and support data collection.

#### Quantitative data management.

Data management will take place at CeSHHAR Zimbabwe under the direction of [name] and [name]. JD will be responsible for all data management protocols and quality assurance (QA) processes. Most data on this project will be computer-entered, with appropriate consistency and completeness checks to minimize errors and missing data. This allows data to be transmitted in real time to a central database, thus reducing concerns about data safety and problems with data storage.

#### Qualitative data management.

Audio files and notes taken during interviews will be stored securely in a folder on the server. Only authorised research team members will have access to this folder. All data will be stored securely in a manner proportionate to the volume and the sensitivity of records involved and will ensure compliance

with the CeSHHAR General Data Protection Regulation (GDPR), national and EU guidelines. All identifiers (address, telephone and names) will be stored separately and linked by a project key. They will be archived and released for use only for data linkage that has been approved by the participant and relevant ethical bodies (e.g. MRCZ), and for re-contact, where permission has been given. All identifiers (such as name, date of birth, location) will be removed from all internal analytical products. All identifiers and potentially disclosive information (such as unusual combinations of occupation and location) will be removed from external products. We will have written permission from participants to collect, store and share all types of data.

#### Managing, storing and curating data.

Data will be collected using tablet computers and consecutively uploaded to a cloud. To minimize errors, range checks and skip patterns within data entry screens will be used. The computing system is password protected, encrypted and only accessible to authorised study team members. Any access to the system is automatically recorded. Data will be managed according to International Conference on Harmonisation guidelines for Good Clinical Practices. Participants will receive a unique study identification number recorded on all forms using a pre-printed bar code and QR code. Numbers will be maintained by the data manager on a password protected, secure computer. Data will be uploaded into a password-protected database.

Database files will be exported in Stata format for bi-weekly batch error checking, monthly reporting and analysis by the data manager. Data will be backed-up daily onto a local machine and on an external hard-drive weekly. Audio files will be transcribed into electronic records which will be backed-up on an external hard-drive after each session. All data will be kept confidential, under lock-and-key, accessible only to trained study staff. Participants' data will be identified by an ID number/barcode only, and a link between names and ID numbers will be kept separately under lock-and-key. Paper copies of locator information and consent forms linked to the data through the project-generated identification will be stored in locked file cabinets. Participant locator information will be destroyed within 1 year of the conclusion of the study unless funding for long-term follow-up is sought, and consent forms within five years of the conclusion of the study.

All samples will be labelled by an ID number/barcode that links the samples to the participant's quantitative and qualitative data. Names, contact details, and other personal information will be removed. The results of tests will not be included on the participants' health records. Every effort will be made to keep personal information confidential.

All qualitative data will be collected on digital recording devices. Audio-recorded qualitative data will be transcribed, including relevant non-verbal communications. The audio files will be stored on the principal applicant and research assistant's password-protected laptop computers. No identifying information will be provided to individuals transcribing the data and they will also sign confidentiality agreements. The transcripts will be translated verbatim into English. After translation, interview summaries will be written for each interview – these will be both a descriptive and analytic synopsis of the interview. Names and other personal identifiers will be removed from transcripts before they are entered into NVivo 10, a qualitative data storage and retrieval program. Transcripts will then be coded using the modified coding framework. Codes will be grouped and emerging themes will be identified. Analytic memos will be written for each theme.

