### Qualitative interviews

The longitudinal qualitative subsample of 20 participants will be theoretically selected from the baseline cohort. As part of the mixed method study design, the quantitative analysis will inform the dimensions of the qualitative sample. Key sampling characteristics which emerge as being pertinent for inclusion and exploration within the qualitative sample will be identified from the quantitative analysis. Household circumstances, duration on ART, current regimen (first/second line), mode of transmission may be considered among other characteristics. Theoretical sampling is based on specific characteristics and directed by evolving themes rather than focusing on predetermined populations (25). Our sampling will ensure participants have a wide range of experiences, relevant to answering the research questions.

A sample of 20 participants for in-depth qualitative studies is anticipated to be large enough to ensure a broad coverage of the specific questions and to ensure theme saturation. Given the interview design (enrolment, 6 and 12 months), the proposed sample size (20 x 3 phases) will enable the quantity of data collected to remain manageable (n=60 interviews) within the timeframe to allow thorough and rich analyses. The longitudinal approach will allow the study to capture changes over time with regards to how adolescents understand VL testing. Eight (8) participatory workshops will be conducted with 20 key stakeholders including healthcare workers with direct contact with the ALHIV and have been involved in viral load results counselling and participating clinics.

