### Informed consent

Participants will be provided with accurate information about the study; its purpose, procedure and duration, including known risks and benefits by a research assistant and will have the opportunity to ask questions as part of the informed consent/assent process. Participants will be given at least 72 hours to consider whether they would like to be involved in the study. If the participant is willing to take part in the study, researchers will schedule for an interview. Written informed consent/assent will be obtained from all participants and all adolescents below age 18 years will also have parents/caregivers' consent. All discussions of VL testing will be based on results of DBS testing which is standard of care. Given that plasma VL testing is unlikely to become available it seems potentially undermining of existing treatment services to share these results. Ongoing psychological support will be available through the Africaid Zvandiri programme including with CATS and clinic-based counsellors if any participants get distressed during or after the interviews.

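### The rule keeping test results off health records is not limited to plasma; as written it covers study DBS, chiefly the 6-month result, and conflicts with the Informed consent section

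*Combined protocol and SAP*

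**What the plan says.** Under Managing, storing and curating data, a short paragraph describes how study samples are labelled by barcode and stripped of personal details. It then states: "The results of tests will not be included on the participants' health records". The paragraph makes no distinction between DBS and plasma.

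The samples in question are described in two places. Study design and setting has the random subsample of 100 adolescents undergo "6 monthly finger prick DBS and plasma VL sampling". Quantitative interviews says this group "will provide plasma and DBS samples VL testing at enrolment, 6 and 12 months".

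The Informed consent section takes a different line for the two sample types. On DBS: "All discussions of VL testing will be based on results of DBS testing which is standard of care". On plasma: "Given that plasma VL testing is unlikely to become available it seems potentially undermining of existing treatment services to share these results".

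Study design and setting also says that treatment history and viral load, including the values at enrolment and 12 months, will be taken from clinic records. Under Aim 3 it plans "longitudinal qualitative interviews at enrolment, 6 and 12 months after receiving their VL result" and adds: "Interpretations of how the VL results are described to ALHIV by clinic staff will also be explored". The inclusion criteria require a viral load below 1000.

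**The concern.** Participants enter with a viral load below 1000. A later study DBS of 1000 or more is a loss of suppression, seen on the type of test that the clinics themselves use. Finding such interim changes is the purpose of the first objective, so the study should expect to meet them if they occur.

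A data manager or laboratory following the data-management sentence as written would not put that result on the health record. The adolescent might still be told, because discussions are to rest on DBS results. But the clinic that manages treatment would have no entry to act on. This matters most midway between routine annual tests, when the clinic may have no recent result of its own.

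**Working it through.** The plan states no figure on this point, so the check is a comparison of texts and a count of the results affected.

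**1. Scope of the rule.** The sentence speaks of tests without qualification, in a paragraph that opens by referring to every study sample. Study samples are both DBS and plasma. On its wording the rule covers both.

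**2. Consistency with the Informed consent section.** That section gives one reason for not sharing results: plasma testing is unlikely to become available, and sharing its results could undermine existing services. Neither part of that reason applies to DBS, which the same section calls standard of care. The plan's own rationale therefore supports a rule for plasma only, while the rule it states covers everything. Neither section refers to the other or says which prevails.

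**3. Whether another section supplies a route to the clinic.**
- The clinic-record data in Study design and setting flow from clinic to study, not back.
- The interview text under Aim 3 assumes that participants receive a viral load result and that clinic staff describe results. It does not say whether these are routine or study results. It concerns the 20 qualitative participants; Qualitative interviews says: "The longitudinal qualitative subsample of 20 participants will be theoretically selected from the baseline cohort".
- The reporting clause under Child protection and safeguarding concerns illegal or reportable activities, not viral loads.
- The support clause under Informed consent concerns distress during or after interviews.
- Samples carry only an identifier, and the link to names is held separately. A result therefore does not reach the clinic unless someone re-identifies and sends it. No visible text assigns that step.

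**4. How many results are exposed.**
- Study DBS results planned: 100 participants × 3 visits = 300.
- At visits where a routine viral load is expected in the clinic record (enrolment and 12 months): 100 × 2 = 200.
- Remaining, at 6 months: 300 − 200 = 100.

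These are maxima, assuming no missed visits. The number of the 100 that would be 1000 or more cannot be derived, because the plan gives no rate.

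**The case against.** The strongest reply is that the intent is clear enough. The Informed consent section makes DBS the basis of all viral load discussions and argues only for withholding plasma. Aim 3 describes fluctuation as measured by standard-of-care DBS and expects some participants to learn of a high value. The disputed sentence sits among labelling and confidentiality provisions. It bars an entry on the record; it does not forbid telling the clinic. On this view only one loosely worded sentence is at fault.

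Most of that stands as a reading of intent. It does not remove the conflict, because staff follow the stated rule and nothing in the other sections limits it. Telling an adolescent a result is also different from placing it before the clinic responsible for treatment.

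The second reply is that the consent and assent pages are not available for review and may contain a return-of-results or referral step. This also stands. A reader might infer that the plan has no way of telling the clinic about a high study DBS. The documents do not support that; they show only that no such step appears in the visible text. If the consent pages do contain one, the data-management sentence would still need to be brought into line.

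The third reply is that routine viral loads at enrolment and 12 months reach the study from clinic records, so those visits are largely covered. This is right, and it is why the exposure is put mainly at the 6-month visit.

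**Conclusion.** The point holds as a conflict between a stated rule and the plan's own rationale. Followed literally, the rule keeps up to 100 six-month study DBS results off the health record, including any that show loss of suppression. It should be corrected.

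The count rests on two assumptions: all 100 attend at 6 months, and routine enrolment and 12-month results are in the clinic records as the plan expects.

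Two stronger readings are tempting and are not supported. One is that the study deliberately withholds DBS results; the Informed consent section and Aim 3 point the other way. The other is that a given number of adolescents would be harmed, or that harm is probable. The plan gives no rate of DBS results at 1000 or more, and a result missing from the record does not show that nobody acted on it.

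**What to change.** 1. In Managing, storing and curating data, replace the sentence with wording to this effect: *Plasma viral load results are kept off the health record; study DBS viral load results are entered on it.*
2. In Informed consent, add: *Any study DBS viral load of 1000 or more is passed promptly to the treating clinic for standard-of-care management.* The team should set a time limit that the clinics can meet.
3. Confirm that the consent and assent text says the same.

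No extra testing is needed. The costs are re-identification through the existing link between names and study numbers, some staff time, and possibly an ethics notification. The last arises because Qualitative data management releases identifiers only for linkage approved by the participant and the ethics bodies, or for re-contact where permission was given.

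There is one consequence for the analysis. If the clinic acts on a high 6-month DBS, the 12-month viral load may change as a result, and this should be noted when fluctuation over the year is reported.
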